5.3.2.2 Alcohol Restrictions

Participants will refrain from consumption of alcohol 24 hours prior to the prestudy and poststudy visits and from 24 hours prior to and after study drug administration in each treatment period. At all other times, alcohol consumption is limited to no more than approximately 3 alcoholic beverages or equivalent (1 glass is approximately equivalent to:

beer [354 mL/12 ounces], wine [118 mL/4 ounces], or distilled spirits [29.5 mL/1 ounce]) per day.

5.3.2.3 Tobacco Restrictions

Participants will not be permitted to smoke 24 hours prior to and on the day of dosing. At all other times, participants will follow the smoking restrictions (and if applicable, the use of nicotine/nicotine-containing products) defined by the Clinical Research Unit (CRU).

5.3.3 Activity Restrictions

Participants will avoid unaccustomed strenuous physical activity (ie, weight lifting, running, bicycling, etc.) from the prestudy (screening) visit until administration of the initial dose of study drug, throughout the study (including washout intervals between treatment periods) and until the poststudy visit.

5.4 Screen Failures

Screen failures are defined as participants who consent to participate in the clinical study but are not subsequently randomized or assigned an allocation number in the study. A minimal set of screen failure information may be included, as outlined in the electronic case report forms (eCRF) entry guidelines. Minimal information may include demography, screen failure details, eligibility criteria, and any AEs or SAEs meeting reporting requirements.

5.5 Participant Replacement Strategy

If a participant discontinues from study intervention OR withdraws from the study a replacement participant may be enrolled if deemed appropriate by the investigator and Sponsor. The replacement participant will generally receive the same intervention or intervention sequence (as appropriate) as the participant being replaced. The replacement participant will be assigned a unique treatment/randomization number. The study site should contact the Sponsor for the replacement participant's treatment/randomization number.

The replacement participant may begin dosing at the subsequent dose level for that panel, based on investigator and Sponsor review and discussion.

6 STUDY INTERVENTION

Study intervention is defined as any investigational intervention(s), marketed product(s), placebo, or medical device(s) intended to be administered to a study participant according to the study protocol.

Clinical supplies, study intervention(s) provided by the Sponsor, will be packaged to support enrollment and replacement participants as required. When a replacement participant is required, the Sponsor or designee needs to be contacted prior to dosing the replacement supplies. Clinical supplies will be affixed with a clinical label in accordance with regulatory requirements.

6.1 Study Intervention(s) Administered

The study intervention to be used in this study is outlined in [Table 2](#).

Table 2 Study Interventions

Arm Name	Arm Type	Intervention Name	Intervention Type	Dose Formulation	Unit Dose Strength(s)	Dosage Level(s)	Route of Administration	Regimen/ Treatment Period/ Vaccination Regimen	Use	IMP/ NIMP	Sourcing
Part 1	Placebo Compar ator	Placebo	Drug	Dry Powder	0 µg	0 µg	Inhalation	One time in each period	Placebo	IMP	Sponsor
Part 1 Periods 1-3	Experi mental	MK-5475	Drug	Dry Powder	15 µg, 60 µg	120 µg, 165 µg, 240 µg	Inhalation	Each dose will be given only 1 time	Experi mental	IMP	Sponsor
Part 2 Periods 1-3	Experi mental	MK-5475	Drug	Dry Powder	15 µg, 60 µg	240 µg, 300 µg, 360 µg	Inhalation	One time in each period	Experi mental	IMP	Sponsor
Part 2 Periods 1-3 Panel D	Experi mental	MK-5475	Drug	Dry Powder	60 µg	120 µg, 480 µg	Inhalation	One single dose in a period	Experi mental	IMP	Sponsor
The classification of Investigational Medicinal Product (IMP) and Non-Investigational Medicinal Product (NIMP) in this table is based on guidance issued by the European Commission and applies to countries in the European Economic Area (EEA). Country differences with respect to the definition/classification of IMP/NIMP may exist. In these circumstances, local legislation is followed.											

These supplies are being provided as open label bulk supplies and will be assigned and dispensed by the unblinded pharmacist at the site.

All supplies indicated in [Table 2](#) will be provided per the "Sourcing" column depending upon local country operational requirements. If local sourcing, every attempt should be made to source these supplies from a single lot/batch number where possible (eg, not applicable in the case where multiple lots or batches may be required due to the length of the study, etc).

Refer to Section 8.1.8 for details regarding administration of the study intervention.

6.2 Preparation/Handling/Storage/Accountability

6.2.1 Dose Preparation

Specific calculations or evaluations required to be performed in order to administer the proper dose to each participant are outlined in a separate document provided by the Sponsor. The rationale for selection of doses to be used in this study is provided in Section 4.3.

MK-5475 and placebo for inhalation will be dosed per the instructions outlined in the Study Operations Manual.

6.2.2 Handling, Storage, and Accountability

The investigator or designee must confirm appropriate temperature conditions have been maintained during transit for all study intervention received, and any discrepancies are reported and resolved before use of the study intervention.

Only participants enrolled in the study may receive study intervention, and only authorized site staff may supply or administer study intervention. All study interventions must be stored in a secure, environmentally controlled, and monitored (manual or automated) area in accordance with the labeled storage conditions with access limited to the investigator and authorized site staff.

The investigator, institution, or the head of the medical institution (where applicable) is responsible for study intervention accountability, reconciliation, and record maintenance (ie, receipt, reconciliation, and final disposition records).

For all study sites, the local country Sponsor personnel or designee will provide appropriate documentation that must be completed for drug accountability and return, or local discard and destruction if appropriate. Where local discard and destruction is appropriate, the investigator is responsible for ensuring that a local discard/destruction procedure is documented.

The study site is responsible for recording the lot number, manufacturer, and expiry date for any locally purchased product (if applicable) as per local guidelines unless otherwise instructed by the Sponsor.

The investigator shall take responsibility for and shall take all steps to maintain appropriate records and ensure appropriate supply, storage, handling, distribution, and usage of study interventions in accordance with the protocol and any applicable laws and regulations.

6.3 Measures to Minimize Bias: Randomization and Blinding

6.3.1 Intervention Assignment

Participants will be assigned randomly according to a computer-generated allocation schedule. A sample allocation schedule is provided in [Table 3](#) below.

Table 3 Sample Allocation Schedule

Panel A ^a					
Participant (N)	Part 1 Period 1	Part 1 Period 2	Part 1 Period 3	Part 2 Period 2	Part 2 Period 3
N=2	120µg	Placebo	240 µg	240µg	240µg
N=2	120µg	165µg	Placebo	240µg	240µg
N=2	120µg	165µg	240µg	240µg	240µg
N=2	Placebo	165µg	240µg	240µg	240µg

^a The participants in Panel A will be randomly assigned.
 A total of 20 participants will participate in Part 2 (Panels A+B+C)

Panel B

Participant (N)	Part 2 ^a Period 1	Part 2 ^a Period 2	Part 2 ^a Period 3
N= 4	300 µg	360 µg	360 µg

Panel C

N = 16 ^b	300 µg	360 µg	360 µg
---------------------	--------	--------	--------

Panel D

N=7 ^c	480 µg	120 µg	120 µg
------------------	--------	--------	--------

^a A total of up to 24 participants will participate in Part 2. (Panels A+B+C+D)

^b The sample size for Panel C may be adjusted depending on the number of participants from Panel A that continue into Part 2 and the start of Panel D. Panel C will not exceed 16 evaluable participants. Participants in Panels B and C will be non-randomly assigned.

^c The sample size for Panel D may be adjusted and will be dependent upon the final number of participants that are enrolled in Panel C. Panel D will not exceed 8 evaluable participants. Participants in Panel D will be non-randomly assigned.

6.3.2 Stratification

No stratification based on age, sex, or other characteristics will be used in this study.

6.3.3 Blinding

In Part 1 (Panel A) of this study, a double-blinding technique will be used. MK-5475 and placebo will be packaged identically so that blind is maintained. The participant, the investigator, and Sponsor personnel or delegate(s) who are involved in the study intervention administration or clinical evaluation of the participants are unaware of the intervention assignments. Part 2 of this study is conducted as open label; therefore, the Sponsor, investigator, and participant will know the intervention administered.

See Section 8.1.10 for a description of the method of unblinding a participant during the study should such action be warranted.

6.4 Study Intervention Compliance

Interruptions from the protocol-specified treatment plan require consultation between the investigator and the Sponsor and written documentation of the collaborative decision on participant management.

6.5 Concomitant Therapy

Medications or vaccinations specifically prohibited in the exclusion criteria are not allowed during time periods specified by this protocol for that medication or vaccination. If there is a clinical indication for any medications or vaccinations specifically prohibited, discontinuation from study intervention may be required. The investigator should discuss any questions regarding this with the Sponsor Clinical Director. The final decision on any supportive therapy or vaccination rests with the investigator and/or the participant's primary physician. However, the decision to continue the participant on study intervention requires the mutual agreement of the investigator, the Sponsor, and the participant.

Listed below are specific examples of permitted (but are not limited to) concomitant therapy or vaccination:

1. Paracetamol/acetaminophen for minor ailments without sponsor consultation.
2. Angiotensin converting enzyme inhibitors (e.g., enalapril).
3. Angiotensin receptor blockers (e.g., losartan).
4. Certain calcium channel blockers (e.g. amlodipine) not being used for the treatment of PAH based on vasoreactivity testing.
5. Trimetazidine.
6. Mineralcorticoid receptor antagonists (e.g. spironolactone, eplerenone)
7. Oral hypoglycemic agents
8. Diuretics.

9. Digoxin
10. Beta-blockers.
11. Aspirin, warfarin, low-molecular weight heparin. Anticoagulation management and risks with regard to performance of the RHC will be managed according to the investigator's clinical judgment.
12. Local anesthetic (e.g. lidocaine) when performing RHC insertion procedure per site SOPs.
13. If needed for the RHC period, intravenous sedatives (e.g., midazolam) or analgesics (e.g., fentanyl) may be given preferably before the procedure and may be used judiciously during the procedure per standard of care.

All permitted prescribed medications may be taken on the morning of the RHC/FRI.

Listed below are specific examples of prohibited concomitant therapy or vaccination:

1. PDE5 inhibitor for PAH; sildenafil or vardenafil taken up to 24 hours prior to dosing of study drug; tadalafil taken within 7 days of anticipated dosing. PDE5 inhibitor treatment may be initiated after 2 days have elapsed from the time of MK-5475 dosing.
 2. sGC activator for PAH taken up to 24 hours prior to dosing of study drug. sGC activator may be initiated after 2 days have elapsed from the time of MK-5475 dosing.
 3. Nitrate taken up to 24 hours prior to dosing of study drug. Nitrates may be initiated after 2 days have elapsed from the time of MK-5475 dosing.
 4. Inhaled prostacyclin taken up to 24 hours prior to dosing of study drug.
 5. Immediate release diltiazem taken up to 24 hours or extended release diltiazem taken up to 48 hours prior to dosing of study drug. Diltiazem may be initiated after 2 days have elapsed from the time of MK-5475 dosing.
 6. ERAs (e.g. bosentan, ambrisentan, macitentan) taken up to 24 hours prior to dosing of study drug. ERAs may be initiated after 2 days have elapsed from the time of MK-5475 dosing.
 7. Verapamil
- **Note: A medication should not be stopped for the purposes of meeting study inclusion criteria. However, the decision to stop/interrupt medication is based on the investigator's judgment.**

6.5.1 Rescue Medications and Supportive Care

Clinical Research Units (CRUs) will be staffed with medically trained personnel with appropriate access to full service acute-care hospitals to facilitate rapid institution of medical intervention. Sites will use their standard operating procedures to manage any acute hemodynamic changes as deemed clinically appropriate (e.g. Trendelenberg position, intravenous fluids).

6.6 Dose Modification (Escalation/Titration/Other)

In Part 1 and Part 2, all dose escalation decisions will be made jointly by the investigator and the Sponsor. Each dose escalation decision may occur after at least 4 evaluable participants in Part 1 (all periods) and 4 evaluable participants in Part 2, Period 1 have completed the previous dose level.

Dose escalation decisions will be based on key safety variables including, vital signs, 12-lead ECG, laboratory safety tests, AEs, and PFTs from the previous dose levels up to at least 24 hours. Pharmacokinetic data may be included in the dose escalation decisions (Section 8.6).

If, as judged by the Sponsor and investigator, the safety and tolerability data do not justify dose escalation, the dose will not be increased as planned. Instead, participants may:

- Receive the same dose level to further explore safety and tolerability at that level,
- Receive a lower dose of the study intervention,
- Receive the same or lower dose as a divided dose,
- Receive a lower dose with or without food, or
- Dosing may be stopped.

Participant discontinuation criteria are outlined in Section 7.

6.6.1 Stopping Rules

The following stopping rules will be employed during the conduct of this study.

If any of the below stopping rules are met, the study will be paused and no further dosing will occur until the Sponsor has reviewed the totality of data available. In order to continue the study (upon joint agreement with the Sponsor and investigator), a substantial amendment will be submitted for approval.

1. An individual participant reports a Serious Adverse Event considered related to the study drug by the investigator.
2. Two (2) or more participants within a Panel (at the same dose level) report Severe Non-serious Adverse Events considered related to the study drug by the investigator.

If any of the below stopping rules are met, subsequent higher doses will be lowered based upon joint agreement of the Sponsor and investigator in order for the study to continue.

Panel wide stopping criteria

- a. Should the emerging PK (mean) data indicate that the maximum clinical exposure (C_{max} or AUC), as defined in Section 4.3 will be exceeded, subsequent higher doses will be adjusted based upon joint agreement of the Sponsor and investigator.

1. Individual stopping criteria:

- a. Hemodynamic changes that exceed the pre-specified limitations (See Appendix 10)

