4.3.1 Starting Dose for This Study

Because MK-5475 is delivered via the inhaled route, calculations for the human equivalent dose (HED) in the lung are used to set dosing guidelines. For dogs, the HED for the NOAEL dose of 0.02 mg/kg is adjusted for the dog weight of 10 kg and the lung deposition factor of 25% to yield a lung exposure of 50 µg ($20 \mu\text{g}/\text{kg} * 10 \text{ kg} * 0.25 = 50 \mu\text{g}$). This is adjusted for the presumed dog lung size of 100 g to yield an estimated lung burden of 0.5 µg/g. Adjusted for human lung size, with a presumed weight of 1000 g, and assuming 100% deposition in humans, the human delivered dose corresponding to the dog NOAEL would be 500 µg.

The starting dose for this study will be 120 µg inhaled in a single dose, allowing approximately a 4-fold safety margin below the NOAEL. In terms of systemic exposure, at this dose, the observed systemic AUC 0-24h was 0.663 nM*hr, which is approximately 1/7th of the systemic NOAEL of 1-month dog toxicology exposure level of 4.5 nM*hr AUC 0-24h. Because the 1-month dog NOAEL was set according to a local finding rather than a systemic finding, and no systemic effects of this compound have been observed except for hemodynamic changes at much higher exposures in preclinical species, this would provide an adequate safety margin. Higher doses have already been administered to humans in the other studies for this compound, with acceptable safety, tolerability, and pharmacokinetic data.

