4.3.2 Maximum Dose/Exposure for This Study

As above, because of the inhaled route of delivery, estimated lung burden was used to determine the maximum allowable exposure based on the lung burden at the dog NOAEL dose. As demonstrated, the dog NOAEL dose corresponds to a delivered human dose of 500 µg. However, in general there were few preclinical findings in either rat or dog safety studies. The NOAEL dose in dogs was 0.02 mg/kg/day; at the three-fold higher dose of 0.06 mg/kg/day, only mild focal bronchial artery thickening was observed, that occurred in one animal in the study.

For the studies in healthy volunteers, the maximum human dose was 240 µg, which provided a ~2-fold safety margin below the NOAEL. In accordance with EMA guidance for first-in-human studies (*Guideline on Strategies to Identify and Mitigate Risks for First in Human and Early Clinical Trials with Investigational Medicinal Products*), this conservative safety margin was applied because the study involved healthy participants. At this dose level, the compound was well tolerated and all safety data was within normal parameters. In addition, the observed pharmacokinetic data established that systemic exposures to the compound were well below the systemic NOAEL level established in dogs.

Having established the tolerability of 240 µg in normal healthy participants, the present study will involve participants in the target population for this therapy. The maximum dose will be advanced to a maximum of 480 µg, which is below the NOAEL dose. The preclinical finding that was noted in dogs appears to be due to a vasoactive pharmacological effect within the

lung, presumably vasodilation induced by MK-5475. Since pulmonary hypertension patients suffer from chronic vasoconstriction, it is likely that they would be better able to tolerate acute vasodilation of blood vessels in the lung without harmful sequelae than healthy participants. In addition, we note that although 100% deposition in humans is assumed in these calculations, the true deposition based on the fine particle fraction is lower (~30-60%), affording an additional safety margin. Therefore, the true lung exposure will be lower than projected above. Thus, a less conservative safety margin is appropriate in patients than in healthy participants, as these participants may potentially benefit directly from development of an additional therapy for their disease.

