Finally, although systemic exposure is considered less relevant for inhaled compounds, based on the observed PK data from the prior study, it was initially projected that systemic exposure will also be approximately 2-fold below the observed AUC 0-24h of 4.5 nM*hr from the dog NOAEL dose at the 240 µg dose. Based on the initial PK data observed in this study for participants in Panel A, the observed systemic PK at a dose of 240 µg was substantially lower than projected, with AUC 0-24h of 1.42 nM*hr. Given the low gastrointestinal bioavailability of this compound, and the observed direct proportionality between delivered dose and systemically measured PK, this reduced exposure was thought to be related to the decreased ability of diseased patients to generate adequate inhaled exposure compared with healthy subjects (as the lung deposition of inhaled DPI compounds is directly affected by the inspiratory flow generated by the subject). As the dose in this study was increased to 300 and then 360 µg, subsequent participants have exhibited higher exposures. In order to further explore the relationship between systemic exposure and delivered dose at higher doses, the maximum dose will be increased in this study to 480 µg. At this dose, the resulting systemic exposure is projected to be approximately 3.5nM*hr AUC 0-24h. While participants may exceed the NOAEL systemic exposure, this exposure was set on the basis of a local finding in the lung in a 30-day toxicology study. In contrast, the finding which was used to set the NOAEL is expected to be driven by lung burden, which at this dose remains below the NOAEL dose of 500 µg. While higher systemic exposures from a single dose may lead to hemodynamic changes, such changes were only observed in preclinical species at systemic exposures far above the NOAEL exposure in pharmacology studies. No evidence of any impact on systemic hemodynamics including heart rate or blood pressure has been observed thus far in any clinical study of MK-5475, and given the short systemic half-life of this compound, it is expected that any such change after a single dose of compound would be self-limited. Finally, a subsequent 3-month GLP toxicology study showed that the finding used to establish the NOAEL was no longer present in a longer duration study.

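### The individual hemodynamic stopping rule has three different consequences across Section 6.6.1 and Appendix 10 and a diastolic limit that overlaps the entry range; the companion exposure rule cites a limit Section 4.3 does not identify

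*Combined protocol and SAP*

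**What the plan says.** The second group of rules in Section 6.6.1 has one stated effect: "subsequent higher doses will be lowered based upon joint agreement of the Sponsor and investigator in order for the study to continue". Two criteria follow.

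- **Individual:** "Hemodynamic changes that exceed the pre-specified limitations (See Appendix 10").
- **Panel-wide:** this criterion concerns mean PK and a ceiling on AUC or Cmax. Its wording is: "as defined in Section 4.3 will be exceeded, subsequent higher doses will be adjusted based upon joint agreement of the Sponsor and investigator".

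Appendix 10 (Section 10.10) defines the individual criterion. It describes what follows in two places. Its opening paragraphs stop further escalation for that participant and allow withdrawal, or re-challenge at the same or a lower dose, with re-challenge only after the investigator and sponsor confer. Its later definition of a sustained change says the participant's dosing ends. Among the listed values is a resting diastolic pressure below 50 mmHg.

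Section 5.2, exclusion 22, excludes systolic pressure below 100 mmHg, diastolic pressure below 40 mmHg or heart rate above 100/min. Section 7.1 lists the reasons for mandatory discontinuation of study intervention and makes discontinuation permanent.

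Section 4.3.1 compares the exposure at 120 µg with the dog NOAEL, "which is approximately 1/7th of the systemic NOAEL of 1-month dog toxicology exposure level of 4.5 nM*hr AUC 0-24h". In Section 4.3.2, "estimated lung burden was used to determine the maximum allowable exposure based on the lung burden at the dog NOAEL dose". For 480 µg, "the resulting systemic exposure is projected to be approximately 3.5nM*hr AUC 0-24h".

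**The concern.** A stopping rule should give one answer when it is met. Here the investigator finds three, depending on which paragraph is open.

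This matters most where no dose increase lies ahead. Within Part 2, Table 1 has only one step up: 300 to 360 µg in Panels B and C. Panel A stays at 240 µg and Panel D goes from 480 µg down to 120 µg. Panel D's RHC period is also the only planned source of PVR data at 120 µg, so the reading chosen affects who contributes to the primary pharmacodynamic endpoint at that dose.

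The diastolic criterion raises a separate question: whether a participant admitted under the entry criteria can be stopped for a value that was already present before dosing.

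The exposure rule is a smaller matter. It sends the reader to Section 4.3 for a limit that is not labelled there.

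**Working it through.** **Step 1. Consequences set side by side, for a Panel D participant with a sustained finding after 480 µg.**

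| Source | Consequence | Effect on the 120 µg periods |
|---|---|---|
| Section 6.6.1 | Later higher doses are lowered | None; no higher dose remains |
| Appendix 10, opening paragraphs | Escalation halted; withdrawal, or re-challenge at the same or a lower dose after consultation | Open: dosing at 120 µg is possible, and so is withdrawal |
| Appendix 10, definition of sustained change | Dosing ends | Not dosed in the FRI or RHC period |
| Section 7.1 | Hemodynamic criteria are not among the mandatory reasons; any discontinuation is permanent | Unsettled: if ending dosing counts as discontinuation, re-challenge is barred |

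The first and third rows cannot both be followed. The second and third stand in the same appendix.

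For scale, one participant is 1/7 = 14% of Panel D at the maximum in Table 1 and Section 4.1, or 1/8 = 12.5% at the evaluable cap in the notes to Table 3. This is a unit of size and not a forecast of losses.

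**Step 2. Entry limits (exclusion 22) against absolute stopping limits (Appendix 10), low-pressure and high-rate side.**

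- Systolic: entry at 100 or above, stop below 90. 100 − 90 = 10 mmHg of separation.
- Heart rate: entry at 100 or below, stop above 120. 120 − 100 = 20 bpm of separation.
- Diastolic: entry at 40 or above, stop below 50. 40 − 50 = −10, an overlap of 10 mmHg.

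Only diastolic pressure overlaps. For heart rate and systolic pressure the list also has criteria expressly relative to the predose baseline (a rise of at least 25 bpm, a fall of more than 25 mmHg). The diastolic line has no such counterpart.

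Take a participant with a diastolic pressure of 45 mmHg before dosing and at the 30, 60 and 90 minute rechecks. The change is 45 − 45 = 0. The entry criterion is met (45 is not below 40), and every recheck is below 50. The operational test in Appendix 10 asks whether the parameters are exceeded at all three rechecks, and the answer is yes. The 90-minute condition therefore does not remove the overlap.

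**Step 3. What Section 4.3 offers as an exposure limit.**

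- Delivered dose at the dog NOAEL, reproduced: 20 µg/kg × 10 kg × 0.25 = 50 µg; 50/100 g = 0.5 µg/g; × 1000 g = 500 µg. This is a lung-burden figure, not a Cmax or AUC.
- Dog NOAEL AUC0-24: 4.5 nM*hr. The stated one-seventh is reproduced: 4.5/0.663 = 6.8.
- Projected AUC0-24 at 480 µg: about 3.5 nM*hr.
- Cmax: no value is given.

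No AUC is named as the maximum. Section 2.2.3 follows geometric means against 4.5. The highest group mean is 4.28 nM*hr, at 360 µg: 4.28/4.5 = 0.951, or 5% below. On that benchmark the rule has not been met.

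**The case against.** **Individual rule.** Section 6.6.1 refers to Appendix 10, so the appendix can be taken as the governing text. Its two statements can then be combined: dosing ends by default, and re-challenge is an exception after consultation. That is workable, but the appendix does not say it, and Section 7.1 leaves open whether such an ending is permanent. The absence of these criteria from the mandatory list argues against permanence; the judgement-based reason of unnecessary risk could still bring a case in.

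On diastolic pressure, Section 6.6.1 speaks of changes, and Appendix 10 speaks of sustained change, compares with the predose baseline and lets each participant's own values set the limit. A baseline-relative reading is therefore arguable. It is not what the operational test asks.

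It is also fair that no distribution of diastolic pressure is given, so no frequency can be claimed, and that Section 5.5 allows replacement.

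**Exposure rule.** Several stronger readings are tempting, and the documents do not support them.

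- *That 3.5 is a rival limit which 4.28 already breaches.* Section 4.3.2 offers 3.5 as the exposure expected at 480 µg. Scaling the 300 µg means gives 2.08 × 480/300 = 3.33 and 2.35 × 480/300 = 3.76, which agrees with a projection. A cap set at the expected mean would make little sense, and the background and dose sections benchmark against 4.5.
- *That 4.5 cannot be the limit because it may be exceeded.* The text, "While participants may exceed the NOAEL systemic exposure, this exposure was set on the basis of a local finding in the lung", concerns participants, while the rule concerns means.
- *That the top 360 µg mean predicts a breach at 480 µg.* The 360 µg periods have sparse PK sampling (FRI) or sampling that stops at 4.5 hours (RHC).
- *That Section 6.6 contradicts Section 6.6.1.* "Pharmacokinetic data may be included in the dose escalation decisions (Section 8.6") is a general permission; the stopping rule is conditional, and PK reviews are scheduled in Table 1 and Sections 4.1 and 8.11.2.
- *That the lack of a required PK action at 480 µg is a defect.* An escalation rule has nothing further to act on at the top dose. Sections 4.1, 4.4 and 8.11.6 leave discretionary routes open.

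**Conclusion.** The individual rule does not hold together as written. Its consequence for one event ranges from nothing required to the end of dosing, and in Panel D that range covers whether the participant is dosed in the 120 µg FRI and RHC periods. The diastolic overlap of 10 mmHg is certain as arithmetic. Whether it produces a stop depends on whether a change from baseline is required, which the text leaves open.

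The exposure point is a missing label. The likely benchmark of 4.5 nM*hr is an inference from Sections 2.2.2, 2.2.3 and 4.3, and against it the observed group means do not breach.

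The number of participants affected is unknown, and neither a loss of precision nor a harm is claimed. The contradiction within Appendix 10, and between it and Section 6.6.1, needs no assumption.

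**What to change.** - Reconcile Sections 6.6.1, 7.1 and Appendix 10 so that a sustained hemodynamic finding has one stated consequence, including whether it counts as permanent discontinuation and how re-challenge fits.
- Reconcile exclusion 22 with Appendix 10 on the diastolic entry and stopping values, and state whether a change from the predose baseline is required.
- Reconcile Section 6.6.1 with Sections 4.3.1 and 4.3.2 so that the exposure limit it refers to is identified, for Cmax as well as AUC if both are meant.

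The sponsor decides which values and rules apply. The cost is protocol wording; no new data or analysis is needed.
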